13.3 Sample Size Justification

Sample size for the Allofit IT HXPE Study was estimated using the McHugh and Le method [43] with an alpha (Type I) error level of 0.05, a non-inferiority margin of 5.2% (δ), and an assumed survival rate of 90% at 10 years from ODEP.

The confidence limit approach, as discussed by McHugh and Le [43], can be used to calculate this sample size estimate. Specifically, we infer that the non-inferiority margin provides the absolute precision (5% δ) for the difference between the fixed rate in the historical control group and the rate estimated for the experimental group over the course of the study. Sample size estimation utilizes the following formula:

$$\delta\sqrt{n} = Z_{1-\alpha} \sqrt{\frac{p_{\text{exp}}(1-p_{\text{exp}})}{w_{\text{exp}}} + \frac{p_{\text{HC}}(1-p_{\text{HC}})}{w_{\text{HC}}}}$$

where δ represents the non-inferiority margin, n represents the group size, p_{exp} represents the rate in the experimental group, p_{HC} represents the rate in the historical control group, w_{exp} represents a weight (i.e., allocation weight) to accommodate unequal group size for the experimental group, w_{HC} represents the allocation weight to accommodate unequal group size for the historical control group, and $Z_{1-\alpha}$ represents the value of a standard normally distributed random variable corresponding to a cumulative probability of one minus alpha (0.05).

When adjusting for a ceiling in the calculation, and added attrition rate of 20% there is a sample size requirement of 195 for the experimental group. A sample size of 200 is therefore planned for enrolment in this study.

Sample size was estimated using SAS v. 9.1.3 for Windows.

14 Management of Incurrent Events

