The subject of this clinical investigation is the *Allofit* IT Shell in combination with the *Longevity* Liners in primary total hip arthroplasty. This system consists of a cementless modular Acetabular Shell, a modular liner, and a modular femoral head. The characteristics of this THA system may allow for reduction in wear and osteolysis as compared to other approved and marketed THA systems and thus increase the expected implant life.

6 Study Objectives

The objective of this study is to obtain survival and outcome data on the *Allofit* IT Shell in combination with *Longevity* Liners in primary total hip arthroplasty. This will be done by analysis of standard scoring systems, radiographs and adverse event records. Data will be used to monitor pain, mobility and survivorship, and to confirm the safety and efficacy of the *Allofit* IT with HXPE in primary total hip arthroplasty.

a) Safety:

Will be evaluated by monitoring the frequency and incidence of adverse events (AE), serious adverse events (SAE), adverse device effects (ADE) and serious adverse device effects (SADE)

b) Efficacy:

Will be determined by comparing the overall pain and functional performances (based on the Harris Hip Scoring system), survivorship, subject quality-of-life and radiographic parameters (radiolucencies, osteolysis, subsidence, cup migration, change in cup angle and change in femoral shaft angle) of study subjects who received the *Allofit* IT Acetabular System

a. Pain and Functional Performance:

Measurements will be based on the Harris Hip Scoring (HHS) System [39]

b. Subject Quality-of-Life:

Will be determined by the Oxford Hip Score [42] and the EQ-5D [41]

c. Radiographic parameters:

X-rays will be evaluated for radiolucencies, cup migration, osteolysis, subsidence, and change in cup angle

d. Survivorship:

Based on removal or intended removal of the device and will be determined using the Kaplan-Meier method

The data will meet Zimmer's obligation to collect device vigilance and post market surveillance information for European regulatory bodies.

7 Study Design

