11.8 Follow-up Procedures (Data Collection)

Data required for completion of the pain, functional and quality-of-life evaluations as well as the radiographic evaluations will be collected postoperatively at 6 months (\pm 1 month), 1 year (\pm 2 months), 2 year (\pm 2 months), 3 year (\pm 2 months), 5 year (\pm 2 months), 7 year (\pm 2 months), and 10 year (\pm 2 months). Post-discharge data collection will include, but is not limited to the following:

1. Physical Exam Form
2. Oxford Hip Score Form
3. Patient Activity Questionnaire Form
4. Harris Hip Form
5. Concomitant Medication Record
6. Radiographs Evaluation Form (standing anteroposterior (AP) and standard lateral views of the operative hip)
7. EQ-5D Form
8. Adverse Event Form (if any)
9. Protocol Deviation Form (if any)
10. Explanted Device Form (if any)
11. Study Completion Form (if the case)

Patient follow-up is expected to continue through 10 years of follow-up for each case although it is expected that a few subjects may succumb to other medical problems or otherwise lost to follow-up prior to completion of the 10 years of follow-up. All subject data will be used in the analysis of overall pain and functional performance, survivorship, and radiographic parameters. Data will continue to be collected until the subject completes the study, is lost to follow-up, one or several devices are removed due to revision, or the study is otherwise closed.

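### The sample size of 195 in Section 13.3 cannot be reproduced from its stated inputs, and the section gives two margins and two treatments of the historical control

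*Combined protocol and SAP*

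**What the plan says.** All the sample-size material is in Section 13.3 (Sample Size Justification).

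- **Margin.** The first paragraph gives "a non-inferiority margin of 5.2" per cent. The second says that "the non-inferiority margin provides the absolute precision (5" per cent).
- **Rate.** One figure is given: "an assumed survival rate of 90% at 10 years from ODEP". The text does not say whether it is the experimental rate, the historical rate or both.
- **Control.** The precision is "for the difference between the fixed rate in the historical control group and the rate estimated for the experimental group". The printed formula nevertheless contains the term p_HC(1 − p_HC)/w_HC, and w_HC "represents the allocation weight to accommodate unequal group size for the historical control group". Neither weight has a value.
- **Error level.** Alpha is 0.05, and the formula uses the normal quantile at 1 − alpha, so it is one-sided.
- **Result.** After rounding up and with an "added attrition rate of 20% there is a sample size requirement of 195 for the experimental group", 200 subjects are planned. The Synopsis and Sections 7.1 and 8 repeat the 200.

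Two other places bear on how loss to follow-up counts. Section 6 defines survivorship as "Based on removal or intended removal of the device and will be determined using the Kaplan-Meier method". Section 11.8 says "All subject data will be used in the analysis of overall pain and functional performance, survivorship, and radiographic parameters".

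**The concern.** Two statements in Section 13.3 conflict. The margin takes two values, and a rate described as fixed is given a variance. Two further inputs are missing: a second rate and the weights. The conflicts are not cosmetic. In the printed formula with equal weights and 90% for both rates, moving from 5.2% to 5% raises n before attrition from 181 to 195. Keeping or dropping the control variance doubles or halves n.

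The 195 is said to include 20% attrition, yet it equals what the formula gives at 5% with equal weights before any attrition is added. A reader cannot tell whether attrition was left out or whether other inputs were used. This paragraph is the stated basis for following 200 people for 10 years, and it does not establish which margin or which precision that number supports.

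**Working it through.** **Inputs (all from Section 13.3).** Z = 1.645 (one-sided, alpha 0.05); margin δ = 0.052 or 0.05; rate 0.90, so p(1 − p) = 0.09; attrition 20%; results rounded up. The weights and a second rate are not stated. Equal weights of 1 and 90% for both rates are assumed where needed.

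**Formula solved for n.**

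n = Z² × [p_exp(1 − p_exp)/w_exp + p_HC(1 − p_HC)/w_HC] / δ²

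For a fixed benchmark the second term is dropped.

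**Attempt to reproduce 195.**

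| Reading | δ | n before attrition | n/0.8 | n × 1.2 |
|---|---|---|---|---|
| Fixed benchmark | 5.2% | 90.05 → 91 | 113.75 → 114 | 110 |
| Fixed benchmark | 5% | 97.40 → 98 | 122.5 → 123 | 118 |
| Two variances, equal weights | 5.2% | 180.10 → 181 | 226.25 → 227 | 218 |
| Two variances, equal weights | 5% | 194.80 → 195 | 243.75 → 244 | 234 |

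None of the eight figures after attrition is 195. The only 195 is in the last row, before attrition.

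**Two-sided Z (1.96, contrary to the text).** In the same row order, n/0.8 gives 160, 174, 320 and 347, and n × 1.2 gives 154, 167, 308 and 333. None is 195.

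**Undisclosed inputs that would give 195 after attrition.** These examples are assumptions and are not evidence of what was done.
- δ = 5.2%, w_HC = 1.37, n/0.8: 90.05 × (1 + 1/1.37) = 155.8 → 156, and 156/0.8 = 195. A second rate of about 0.93 has a similar effect.
- δ = 5%, w_HC = 1.5, × 1.2: 97.40 × (1 + 1/1.5) = 162.33, and 162.33 × 1.2 = 194.8 → 195. Rounding at both steps gives 196.

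**One-sided precision from 200 enrolled.** With 20% fully lost, 200 × 0.8 = 160 remain.
- Fixed benchmark: 1.645 × √(0.09/160) = 3.90 points; 1.645 × √(0.09/200) = 3.49 points.
- Two variances, equal weights: 1.645 × √(0.18/160) = 5.52 points; 1.645 × √(0.18/200) = 4.93 points.

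With other inputs in the two-variance formula, 160 subjects meet 5.2% only if w_HC is at least about 1.29 or the second rate at least about 0.924. They meet 5% only if w_HC is at least about 1.56 or the second rate at least about 0.938.

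**Attrition that 200 tolerates (two variances, equal weights).** 1 − 181/200 = 9.5% at 5.2%; 1 − 195/200 = 2.5% at 5%.

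**The case against.** The strongest reply has four parts.

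1. **Omission is not contradiction.** The formula provides for unequal weights, and some weights do give 195 after attrition. The figure is therefore unverifiable, not proven wrong. This stands: the match with the pre-attrition result rests on assumed equal weights and 90% for both rates, and it does not prove that attrition was forgotten. It does not rescue the section, because a reader has to guess the inputs.
2. **Fixed may mean set in advance from an outside source.** A variance term would then be a cautious allowance for uncertainty in that source. This is possible, but the text does not say so, and the choice changes n by a factor of two. Likewise, 5% may be a rounded repeat of 5.2%, but the rounding changes n from 181 to 195.
3. **The 160 figure is a complete-case worst case.** Survivorship is by Kaplan-Meier, so subjects lost later contribute until censoring. This stands: with 20% lost, precision lies between the 160 and 200 values. Under the equal-weight two-variance reading that is 4.9 to 5.5 points, a range that contains both margins.
4. **Little depends on the margin.** The study is non-controlled, and Sections 13.1 and 13.2 describe summaries and a survival analysis with no test against the margin. This also stands, and it limits the consequence to the justification itself.

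**Conclusion.** The concern holds. Section 13.3 states two margins, describes the control in a way its formula contradicts, and reports 195 after 20% attrition, which its stated inputs do not give. At n/0.8 the enrolment needed is 114 or 123 with a fixed benchmark (5.2% or 5%), and 227 or 244 with two variances. The latter pair assumes equal weights and 90% for both rates.

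This does not show that 200 is inadequate. Under the section's own description of a fixed rate, 200 is more than enough. Under the equal-weight two-variance reading, 200 falls short of either margin if 20% contribute nothing. The documents do not settle which reading applies, so the precision the study can claim at 160 subjects ranges from 3.9 to 5.5 points. The outcome is an unsupported sample-size justification that should be corrected; no planned hypothesis test fails because of it.

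**What to change.** Keep 200 enrolled and rewrite Section 13.3:

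- Use one margin throughout.
- Make the control description and the formula agree. If the rate is fixed, drop the historical variance term. If not, remove the word fixed and state p_HC, w_exp and w_HC with their source.
- Replace 195 with n before and after 20% attrition from those inputs, and say whether attrition is applied as n/0.8 or × 1.2.
- State the precision at 160 and 200 subjects.

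For a fixed benchmark at 5.2%, the text would give 91 evaluable and 114 enrolled, with 3.9 points at 160 and 3.5 at 200 (at 5%: 98 and 123). If the equal-weight formula with 90% for both rates is kept, it would give 5.5 points at 160 and 4.9 at 200, or say that 200 tolerates 9.5% attrition at 5.2% and 2.5% at 5%. If other weights or a second rate were used, state them and show the step to 195.

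The cost is rewording one section, with no extra patients or visits. The stated precision or attrition allowance may look slightly less favourable under the two-variance reading.

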14.1 Definitions

As defined by EN ISO 14155-1 [1] and ISO 14155-2 [2]:

Adverse Event

An Adverse Event is defined as any untoward medical occurrence in a subject. This definition does not imply that there is a relationship between the adverse event and the device under investigation.

Adverse Event is synonymous with complication or medical event.

Serious Adverse Event

A Serious Adverse Event is defined as an Adverse Event that:

- leads to death,
- leads to a serious deterioration in the health of the subject that
 - 1) resulted in a life –threatening illness or injury,
 - 2) resulted in an impairment of a body structure or a body function,
 - 3) required in-patient hospitalization or prolongation of existing hospitalization,
 - 4) resulted in medical or surgical intervention to prevent permanent impairment to body structure or a body function,
- leads to fetal distress, fetal death or a congenital abnormality or birth defect.

Adverse Device Effect

An Adverse Device Effect is defined as 'any untoward and unintended response to a medical device'. This definition includes any event resulting from insufficiencies or inadequacies in the instructions for use or the deployment of the device. This definition includes any event that is a result of a user error.

Serious Adverse Device Effect

A Serious Adverse Device Effect is defined as 'an Adverse Device Effect that has resulted in any of the consequences characteristic of a Serious Adverse Event or that might have led to any of these consequences if suitable action had not been taken or intervention had not been made or if circumstances had been less opportune'.

14.2 Reporting and Documentation of Adverse Events and Adverse Device Effects

Adverse Events and Adverse Device Effects have to be documented on the Adverse Events Report Form over the whole time of the investigation. Further the outcome of such complications has to be documented and any changes in outcome to be updated during the course of the study.

14.3 Reporting and Documentation of Serious Adverse Events and Serious Adverse Device Effects

Serious Adverse Events and Serious Adverse Device Effects have to be documented on the Adverse Events Report Form over the whole time of the investigation. The outcome of

such complications has to be documented and any changes in outcome to be updated during the course of the study.

14.4 Recommended Revision Procedure

14.4.1 *Revision Methods*

Standard total hip replacement and revision methods will be utilized in the event of a device failure resulting in revision of one or more of the System Components (i.e. acetabular shell, liner, head, or femoral stem).

14.4.2 *Prior to Revision Surgery*

Prior to revision surgery, the Investigator must evaluate the acetabular and femoral components for any evidence of migration, change in cup angle, radiolucencies or osteolysis by comparing the immediate post-operative and most recent post-operative radiographs of the operative hip.

14.4.3 *During the Revision Surgery*

During the revision surgery, the Investigator must carefully inspect the surgical site for any evidence of acetabular or femoral instability, excessive surface wear or the presence of any other acetabular or femoral component damage. If it is believed the acetabular or femoral components are unstable for any reason or damaged in any way, it is recommended the unstable/damaged acetabular or femoral component(s) be removed and revised.

14.4.4 *Explanted Investigational Device Analysis*

In the event of an investigational device revision, all components revised should be returned to Zimmer for analysis. The Investigator must notify the study manager prior to the return of any device.

For used, contaminated devices, immerse the implant in 10 percent neutral buffered formalin, label the implant container to identify the catalog number, Investigator name, Case ID, date of removal, and include a statement indicating the implant is from an IDE study.

Properly prepared specimens are to be sent to:

Zimmer GmbH
International Clinical Affairs
[name]
Cost Center 113505
[name]
[name]
Switzerland

[figure not shown]
Once the analysis is complete, a copy of the report will be maintained in the study subject record by Zimmer International Clinical Affairs and a copy will be sent to the Investigator for his/her study records. A summary of all detailed explant reports will be provided in the Annual Reports.

All SAEs and SADEs have to be reported to the Clinical Study Manager as soon as possible by sending a copy of the Adverse Events Report Form either by fax to or e-mail

to:

Zimmer GmbH
International Clinical Affairs
[name]
P.O. Box
[name]
Switzerland
[contact]
[contact]
[contact]

14.5 Documentation and Reporting Flow Chart

14.6 Patient Withdrawal

Subjects may withdraw from the study at any time. If possible, a final evaluation will be completed for all subjects who no longer wish to participate in this investigational study. The reason for the subject withdrawal must be documented on the Study Completion case report form.

14.7 Lost to Follow-up

Patients will be considered lost to follow-up after they have missed a visit and a reasonable number of attempts to locate and evaluate them have failed. This has to be documented on Study Completion Form. In particular the reason must be documented.

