APPENDIX D	INVESTIGATOR'S CONSENT TO THE CLINICAL INVESTIGATION PLAN..	63

1 Contact Information/ List of Investigators

Sponsor:	Zimmer GmbH
Clinical Investigators:	See Appendix A

Clinical Study Manager:	[name], CRA
On-site Monitoring:	[name], CRA
Data-Management:	Zimmer Warsaw
Statistical Analysis:	Zimmer Warsaw and Winterthur
Quality Assurance:	[name], Director Intl Clinical Affairs

[figure not shown]
2 Study Synopsis

Title:	
Allofit® IT with HXPE in Total Hip Arthroplasty
 
A multi-center, prospective, non-controlled post market surveillance study

Sponsor:	Zimmer GmbH
Objectives/ Endpoints:	
The objectives of this study are to obtain survival and outcome data on the Allofit IT Shell in combination with the Longevity® Liner when used in primary total hip arthroplasty. This will be done by analysis of standard scoring systems, radiographs and adverse event records. Data will be used to monitor pain, mobility and survivorship, and to confirm the safety and performance of the Allofit IT HXPE Bearing System.
 
Safety will be evaluated by monitoring the frequency and incidence of adverse events.
 
Performance will be determined by comparing the overall pain and functional performances, survivorship, subject quality-of-life and radiographic parameters of study subjects who received the Allofit IT HXPE Bearing System.
 
Pain and functional performance will be measured using the Harris Hip Score, survivorship will be based on removal or intended removal of the device, subject quality-of-life will be determined by evaluation of the Oxford Hip Score, and radiographic parameters by analysis of x-rays.

Indication/ Target Popula- tion:	Patients, suffering from severe hip pain and disability requiring total hip arthroplasty, who meet the inclusion/ exclusion criteria (see Section 8).
Study Design:	Multi-center, prospective, non-controlled
Clinical Phase:	Post-market
Number of Sub- jects:	A total of 200 patients will be enrolled in this study
Length of Study:	12 years (2 year enrollment plus 10 years follow-up): follow-up visits at 6 months, 1, 2, 3, 5, 7, and 10 years post-operatively.
Study Device:	Allofit IT Shell in combination with:

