The **Study Completion** Form (form 14) is completed when the patient completes the study. If there is a change to the active participation of a patient in the study, it is necessary to complete this form. Examples include lost-to-follow-up, death, refusal to return for an assessment, or withdrawal from a study.

The **Explanted Device** Form (form 15) is completed by the Investigator or his/her designee and details reason and results on explanted devices.

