11.9 Minimization of Subjects Lost to Follow-up

Subject follow-up is extremely important for the conduct of a clinical study. The expectation is to maintain the highest rate of follow-up compliance possible throughout this study. In an effort to minimize *lost to follow-up* study subjects, the following recommendations and/or study requirements are essential to ensure proper patient selection and compliance:

1. Patient Eligibility: Subjects will be selected according to patient eligibility criteria detailed in Section 8 and are expected to return for all follow-up visits.

2. Patients counseled: Patients will be counseled during the informed consent process on the importance of returning for follow-up visits.
3. Patient Exclusion: Patients who are not willing to return for study required follow-up visits and/or are not willing to comply with the follow-up schedule will not be considered for enrollment in the study.
4. Subject Due Listings: In addition to proper patient selection, Zimmer will provide subject due notices to the sites on a regular basis in order to track each study participant and monitor adherence to the required follow-up visit timeframes. The subject due listings will facilitate scheduling the subjects for their return office visits.
5. Financial Hardship: If during the course of the study it is determined that a subject is experiencing a financial hardship that prevents the subject from returning for follow-up visits, Zimmer should be notified to discuss possible financial assistance which may be available to the subject.
6. Contact Tracking: Attempts to contact subjects will be documented. It is recommended that the first three attempts be made by telephone.

Recommended Contact Attempts

If	then
A response is not received from the three phone calls	The Investigator should send a letter to the subject explaining the follow-up agreement per the informed consent.
A response is not received from the Investigator's letter	The Investigator should send a certified letter to the subject.
A response is not received from the Investigator's certified letter	The Investigator should use any additional contacts provided by the subject to contact the subject.
If all attempts to contact the subject are unsuccessful or the subject is contacted and chooses to withdraw from the study	The Study Completion CRF will be completed and will specify the reason the subject is no longer participating in this study.

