14.9 Termination of the Trial

The study terminates for each patient 10 years after surgery with the final visit. Reasons for an earlier termination can be found in sections 14.6 and 14.7.

In the case of early termination of the study the Investigators have to be informed by the Sponsor. The regulatory authority(ies) and ethic committee(s) shall also be informed according to local and national regulations including the reason for termination.

15 Quality Control and Quality Assurance

The study is conducted in accordance with the Declaration of Helsinki [44] and the ISO 14155 Standard for the Clinical Investigation of Medical Devices part 1 and 2 [1;2].

The Investigator will be required to permit representative(s) of the Sponsor's monitoring team to inspect all Case Report Forms and corresponding sections of the study patients office records and/or hospital original medical records. These audits will be done for quality assurance purposes i.e. verifying adherence to the Clinical Investigation Plan and the completeness and accuracy of the data being entered on the Case Report Forms.

Moreover, local national authorities could audit the sites as well. In this particular case, all documents requested by the auditor(s) have to be available and handed out.

The Clinical Investigation Plan will be provided to all participating study centers. The Investigators will be fully trained in the proper reporting and submission of trial data prior

to patient enrolment. Completed Case Report Forms will be reviewed before entering the data into a central database by the Sponsor.

The Clinical Study Manager is responsible for generating data queries for missing or unclear data if needed. It is the responsibility of the Clinical Study Manager to ensure data quality.

There are regular meetings between the Investigators and Zimmer International Clinical Affairs staff. Written correspondence to all sites is used to inform the Investigators of routine study details and to update them on study status.

16 Ethics and Regulatory

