(DD-MM-YYYY) Device Removal/Reoperation - Date: - -
(DD-MM-YYYY) Death - Date: - -
(DD-MM-YYYY)

General Complications

- 01 Cardiovascular
- 02 Dermatological
- 03 Endocrine
- 04 ENT
- 05 Gastrointestinal
- 06 Genitourinary / Renal
- 07 Hematological
- 08 Infection (non-hip)
- 09 Musculoskeletal (non-hip)
- 10 Neurological
- 11 Oncological
- 12 Pulmonary/Respiratory
- 88 Other General Complication

Hip Related Complications

- 40 Acetabular Implant Failure
- 41 Acetabular Implant Fracture
- 42 Acetabular Implant Loosening
- 43 Deep Vein Thrombosis
- 44 Delayed Wound Healing
- 45 Dislocation
- 46 Femoral Implant Failure
- 47 Femoral Implant Fracture
- 48 Femoral Implant Loosening
- 49 Fracture of Acetabulum
- 50 Fracture of Femur
- 51 Fracture of Trochanter
- 52 Hematoma
- 53 Heterotopic Ossification
- 54 Infection (hip), superficial
- 55 Infection (hip), deep
- 56 Instability
- 57 Nerve Injury/Palsy
- 58 Stem Subsidence
- 59 Subluxation
- 60 Thigh/Groin/Hip Pain
- 61 Trochanteric Bursitis
- 62 Vascular Deficit
- 98 Other Hip Related Radiographic Finding
- 99 Other Hip Related Complication

10. Date Reported to Ethics Committee: - -
(DD-MM-YYYY) Not Required Future ReportInitials of Person Completing Form:

16162

31-AUG-2010

Allofit IT Bearing System

Protocol Deviation

PLEASE COMPLETE ONE FORM PER OPERATIVE SIDE

Form 13

FOR ZIMMER USE ONLY

Patient Initials

Case ID

Date of Surgery - -
(DD-MM-YYYY)

Investigator ID

Operative Side Left
 RightForm Completion Date - - Examination Period: Preop 6 Month 1 Year 2 Year 3 Year 5 Year 7 Year 10 Year

1. Type of Deviation:

- Informed Consent
- Inclusion/Exclusion
- Surgical Procedure
- Missed Visit
- Visit Outside Protocol Window
- Missed X-rays, specify:
 - A/P
 - Lateral
- Incomplete CRFs, specify: _____
- Other, specify: _____

2. Explanation of Protocol Deviation:

3. Date Deviation Occurred: - -
(DD-MM-YYYY)

If missed visit, date is the last day of the protocol allowed window.

4. Date Deviation Reported to Zimmer: - -
(DD-MM-YYYY)

5. Action Required:

6. Does your Ethics Committee require this Protocol Deviation be reported? Yes* No*If Yes, date deviation reported to Ethics Committee: - -
(DD-MM-YYYY) Future reportInitials of Person Completing Form:

31-AUG-2010

43732

Study Completion

PLEASE COMPLETE ONE FORM PER OPERATIVE SIDE

Form 14

FOR ZIMMER USE ONLY

Patient Initials

Case ID

Date of Surgery - - (DD-MM-YYYY)

Investigator ID

Operative Side Left Right

Form Completion Date - -

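### One missed visit plus failed contact closes the case, with no provision to retry at later visits or check implant status remotely, in a study of 10-year survivorship

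*Combined protocol and SAP*

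**What the plan says.** Four sections of the combined protocol and SAP act together.

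- **14.7** sets the trigger: "Patients will be considered lost to follow-up after they have missed a visit and a reasonable number of attempts to locate and evaluate them" prove unsuccessful. The trigger is a single visit. The number of attempts is not fixed and no deadline is given. The Study Completion Form must be filled in.
- **11.8** sets the consequence for data: "Data will continue to be collected until the subject completes the study, is lost to follow-up", among other end points.
- **14.9**, after stating that each patient's study ends at 10 years, adds: "Reasons for an earlier termination can be found in sections 14.6 and 14.7".
- **11.9** recommends three phone calls, a letter, a certified letter and then any additional contacts the patient supplied. If these fail, the Study Completion Form "will specify the reason the subject is no longer participating in this study".

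Two other places bear on the point. The Protocol Deviation Form (Form 13, Appendix B) has a category for a missed visit and says how to date it: "If missed visit, date is the last day of the protocol allowed window". A missed visit alone is therefore a deviation and not an exit. The list of triggers for the Study Completion Form in 10.1 reads: "Examples include lost-to-follow-up, death, refusal to return for an assessment, or withdrawal from a study". It names refusal separately from withdrawal.

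The synopsis schedules "follow-up visits at 6 months, 1, 2, 3, 5, 7, and 10 years post-operatively", which is seven visits.

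**The concern.** A patient who cannot be reached around the 6-month visit can be closed 9.5 years before the endpoint. From then on no section asks the site to do anything further for that case: no new attempt when the next visit falls due, no procedure for taking the patient back, and no way to record implant status without attendance.

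The study aims first at survival data (section 6), and its sample size rests on a 10-year survival rate (13.3). Survivorship turns on whether and when the device was removed or its removal was planned, which a call or a letter can establish. The Oxford, EQ-5D and activity forms are completed by the patient and could be mailed.

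Two things are at stake. Late follow-up time is lost, where a 10-year estimate is thinnest. Censoring may also be informative: if patients who stop attending have more revisions, for example at another hospital, those revisions go uncounted and survivorship looks better than it is.

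**Working it through.** **Inputs from the plan.** Seven visits (synopsis); 10-year survival of 90%, margin of 5.2% (also given as 5%), alpha 0.05, attrition of 20%, 195 required and 200 planned (13.3); Kaplan-Meier (section 6). **Assumptions.** Final loss per visit q, return probability r, and the failure risk ratio RR of lost to retained patients. The plan gives none of these. Deaths are ignored.

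**1. The plan's own figure.** With the 13.3 formula, one-sided Z = 1.645, p = 0.90 in both groups and weights of 1, n = 1.645² × 0.18 / δ².
- δ = 5.2%: 180.1, so 181; with attrition 181/0.8 = 226.25, so 227.
- δ = 5%: 194.8, so 195 before any attrition; with attrition 195/0.8 = 243.75, so 244.

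The stated 195 is not reproduced with attrition included. An undocumented experimental rate of 0.93 with δ = 5.2% gives 156, and 156/0.8 = 195, so the figure cannot be called wrong with certainty. That is a separate matter. Here it means only that the real allowance for loss is uncertain. If 195 is the number before attrition, enrolling 200 leaves room to lose 5.

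**2. Accumulation if loss is final.** The share closed before the 10-year visit is 1 − (1 − q)^6, because a miss at year 10 itself is not caused by the closing rule. The share lost by the end is 1 − (1 − q)^7.

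| q | closed before year 10 | lost over all seven visits |
|---|---|---|
| 2% | 11% | 13% |
| 5% | 26% | 30% |
| 8% | 39% | 44% |

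The planned 20% is reached at q = 1 − 0.8^(1/7) = 3.1% per visit.

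**3. If return is possible.** Let a be the share in contact, starting at 1 and updated at each visit as a(1 − q) + (1 − a)r. In contact at 10 years, of 200:

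| q | final loss | r = 25% | r = 50% | r = 75% |
|---|---|---|---|---|
| 3% | 161.6 | 180.7 | 188.7 | 192.3 |
| 5% | 139.7 | 169.4 | 181.9 | 187.5 |
| 10% | 95.7 | 145.7 | 166.7 | 176.5 |

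**4. Bias in Kaplan-Meier survivorship.** Assume 20% are lost, one seventh of them at each visit, and are censored at the preceding visit (c = 0, 0.5, 1, 2, 3, 5, 7 years). Hazards are constant within each period and true overall failure at 10 years is 10%. Let h be the hazard in retained patients.

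*(a) The lost have RR × h throughout.* Solve 0.8(1 − e^(−10h)) + 0.2(1 − e^(−10·RR·h)) = 0.10. The Kaplan-Meier limit is the exponential of minus the integrated average hazard among those still observed.

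*(b) The lost have h until censoring and RR × h afterwards.* Solve 0.8(1 − e^(−10h)) + (0.2/7) Σ[1 − e^(−h(c + RR(10 − c)))] = 0.10. The Kaplan-Meier limit is e^(−10h).

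| RR | (a) survivorship | (b) survivorship | excess over 90% |
|---|---|---|---|
| 1.5 | 90.6% | 90.6% | 0.6 points |
| 2 | 91.1% | 91.2% | 1.1-1.2 points |
| 3 | 91.8% | 92.1% | 1.8-2.1 points |

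**The case against.** The strongest reply is that the plan is less severe than it looks. Section 14.7 sets no deadline for its attempts, and with gaps of 2 to 3 years between later visits a site need not close a case before the next one falls due. No section bars a closed patient from returning. The 11.9 sequence is substantial and is backed by due listings, counseling and possible financial help. Patients who exhaust it are not simply away for a while, and the same routes may fail again. The Study Completion Form already records the date of last assessment, so a workable censoring date exists. Remote contact cannot supply the investigator-completed Harris Hip Score or the radiographs.

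Most of this stands as a limit on size. It does not remove the point: 11.9 governs one episode of absence, 11.8 ends data collection once a patient is classed as lost, and nothing tells a site to try again.

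Four stronger readings are tempting, and the documents do not support them.

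- *Closure is permanent.* This would be inferred from silence, since no section forbids re-entry.
- *Refusing one assessment ends participation.* Only 10.1 points that way. Neither 11.8 nor 14.9 mentions refusal, 11.9 closes a case only "If all attempts to contact the subject are unsuccessful or the subject is contacted and chooses to withdraw from the study", and Form 14 has no box for a single refused visit. This is a conflict between sections and does not establish a rule.
- *30% would be lost against 5% with temporary absences.* That assumes every absent patient is back at the next visit and charges the year-10 miss to the rule. With r of 25% to 75%, 6% to 15% are still missing.
- *The bias is 0.9, 1.7 or 2.9 points.* This follows from 0.10 − 0.10/(0.8 + 0.2 × RR), which gives lost patients no observed time. Kaplan-Meier keeps their time up to censoring.

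**Conclusion.** The point holds and should be acted on. As written, one missed visit with failed contact closes the case, and the plan makes no provision for learning implant status afterwards.

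The size depends on assumptions. At 5% final loss per visit about 26% are closed before the 10-year visit, and the 20% allowance is used up at about 3.1% per visit. With 20% lost, survivorship is overstated against complete follow-up by 0.6 to 2.1 points for risk ratios of 1.5 to 3, compared with a margin of 5.2 points. That the lost fail more often is a hypothesis; if their risk equals that of the others, the harm is lost late precision only. Renewed contact would recover part of this bias and not all of it.

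**What to change.** In 14.7, 11.8 and 11.9:

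1. Record a missed visit with failed contact on the Protocol Deviation Form, and keep the case open and on the subject due listing.
2. At each later scheduled visit, try contact again. If the patient will not attend but has not withdrawn consent, record implant status (removed or removal planned, with date) by phone or letter, and mail the patient-completed forms.
3. Make the final lost-to-follow-up classification at the end of the study.
4. Censor survivorship at the last date on which the device was known to be in place.
5. Reconcile 10.1, where refusing to return for an assessment triggers the Study Completion Form, with 11.9, where a contacted patient is closed only on choosing to withdraw.

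The cost is protocol wording, some extra phone or mail contact using the due listings already planned, and possibly a check that the consent text allows it. Harris Hip Score and radiographic data will stay missing for patients who do not attend.
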